2.1.4 Presentation of results

2.1.4.1 QPCR VIRAL SHEDDING

qPCR vAUC table will show descriptive statistics and the p-value of the Mann-Whitney U test for comparison of MVA-NP+M1 and placebo (primary analysis). Additionally, a table will report the results of the ANCOVA model, including the least square means per treatment group with 95% CI, least square mean differences (MVA-NP+M1 - placebo) with 95% CI and 2-sided p-value for testing differences between treatment groups.

Log qPCR and culture values and SSC scores will be summarised by means of descriptive statistics at each timepoint. Actual values and changes will be tabulated separately. The adjusted means by treatment group at each timepoint from the MMRM will be tabulated and presented graphically.

A frequency tabulation will show the number and percentage of successful attacks, with exact 95% CI and will also report the Fisher exact p-value for comparison of MVA-NP+M1 and placebo (secondary analysis). A similar table will also be created for virologically confirmed ILI.

For time to start/peak/cessation of viral shedding/feel well enough to go to work, the following results will be reported: number and percentage of events, number and percentage of censored observations, Q1, median and Q3 time with 95% CI and p-value (MVA-NP+M1 vs. placebo) using log-rank test.

Duration of viral shedding and peak viral shedding tables will show descriptive statistics and for peak viral shedding also the p-value of the Mann-Whitney U test for comparison of MVA-NP+M1 and placebo.

A listing will be prepared showing all derived parameters and the log qPCR values.

	Statistical Analysis Plan	
FLU010	Final analysis	Final 3.0 of 15JUN2020

Mean (SE) log qPCR and culture values and SSC overall score over time will be plotted. For all three time to parameters, Kaplan-Meier plots will be prepared.

A list of tables, figures and listings can be found in section 8

2.1.4.2 CULTURE VIRAL SHEDDING

The same viral shedding parameters as calculated based on qPCR values will be calculated based on culture values and will be presented in an identical way.

A list of tables, figures and listings can be found in section 8

2.1.4.3 INFLUENZA SYMPTOMS

Overall, local and general SSC AUC tables will show descriptive statistics and the p-value of the Mann-Whitney U test for comparison of MVA-NP+M1 and placebo. Additionally, a table will report the results of the ANCOVA model, including the least square means per treatment group with 95% CI, least square mean differences (MVA-NP+M1 - placebo) with 95% CI and 2-sided p-value for testing differences between treatment groups.

Overall, local and general SSC scores will be summarised by means of descriptive statistics at each timepoint. Actual values and changes will be tabulated separately. The adjusted means by treatment group at each timepoint from the MMRM will be tabulated and presented graphically.

For time to start/peak/cessation of symptoms/feel well enough to go to work, the following results will be reported: number and percentage of events, number and percentage of censored observations, Q1, median and Q3 time with 95% CI and p-value (MVA-NP+M1 vs. placebo) using log-rank test.

Duration of symptoms and peak symptoms tables will show descriptive statistics and for peak symptoms also the p-value of the Mann-Whitney U test for comparison of MVA-NP+M1 and placebo.

Total days of fever table will show descriptive statistics and the p-value of the zero-inflated Poisson model.

Total mucus production table will show descriptive statistics and the p-value of the Student t-test/Mann-Whitney U test.

A listing will be prepared showing all SSC derived values and scores at each analysis visit. A separate listing will be created for fever and total mucus production, showing total days of fever and body temperature at each analysis visit and total mucus production.

Distinct Mean (SE) plots over time will be created for overall, local and general SSC scores. For all three time to parameters, a Kaplan-Meier plot will be prepared.

A list of tables, figures and listings can be found in section 8

2.2 IMMUNOGENICITY

2.2.1 Available data

T cell response is assessed using a double-colour enzymatic (DCE) ELISpot assay for IFN gamma and granzyme B on the peripheral blood mononuclear cell (PBMC)

SGS	Statistical Analysis Plan	
FLU010	Final analysis	Final 3.0 of 15JUN2020

samples, taken on day 0, day 8 and day 28 of the vaccination period and day -1 and day 28 of the challenge period. For each of IFN gamma and granzyme B, three stimulation antigens will be assessed: NP (4 pools), M1 (2 pools) and a negative control (DMSO). For each pool, the number of spot-forming colonies (SFC) per well (i.e. 200,000 cells) will be reported for two replicate wells.

ELISpot assay results will possibly not be available for the final analysis. In that case, analyses of the T cell response described below will not be done.

Antibody responses are evaluated with micro neutralization (MNT) and hemagglutination inhibition (HI) tests, done at screening (MNT only) and day -1 and day 28 of the challenge period.

2.2.2 *Derivation rules*

T cell response results will be averaged over all replicates within each pool, then background subtracted (set to 0 if negative) and finally added across all pools within each antigen as follows (XX being either NP or M1):

- Background subtracted T cell response result for pool Y of antigen XX (SFC/well) =
$$BG_{sub_{XX^Y}} = \text{average within pool Y of antigen XX} - \text{averaged negative control (DMSO) result}$$
- Background subtracted T cell response result for antigen XX (SFC/ 10^6 cells) =
$$BG_{sub_{XX}} = 5 \times \sum_{n=1}^k \max(BG_{sub_{XX^n}}, 0)$$

(k is the number of pools within the antigen XX)
- Background subtracted T cell response result for NP+M1 (SFC/ 10^6 cells) =
$$BG_{sub_{NP}} + BG_{sub_{M1}}$$

Negative control T cell response results will be averaged over all replicates and multiplied by 5 (to get SFC/ 10^6 cells).

T cell responder status will be derived using the Permutation-based Resampling (PR) method (Hudgens et al., 2004). See also SAS code in appendix. Briefly, for each of the NP and M1 peptide pools, an unadjusted p-value will be calculated by comparing the observed SFCs/well from the corresponding peptide pool replicate wells against the negative control replicate wells using a two-sample t-test. Next, within each antigen (NP or M1) the observed SFCs/well will be permuted across all the peptide pool and negative control wells 100,000 times, with unadjusted p-values calculated for each permuted replication. The lower of the two p-values will be retained as the permutation-adjusted p-value for each replication. Finally, for each of the peptide pools, the permutation-adjusted p-value will be calculated as the proportion of times when the permutation-adjusted p-value is less than the peptide pool-specific unadjusted p-value. This approach can only provide statistically significant results when there is an adequate number of permuted outcomes.

If a permutation-adjusted p-value of any of the pools within the antigen is less than 0.05, then the subject will be considered a responder for that antigen.

	Statistical Analysis Plan	
FLU010	Final analysis	Final 3.0 of 15JUN2020

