Nasal swabs for influenza virus are collected twice a day (at least 8 hours apart) from Day 2 to Day 10 following intranasal challenge, which are tested for influenza PCR and culture. Symptoms of influenza-related infection will be collected from Day 1 to Day 11 of challenge, as will total nasal tissue weight.

Efficacy: Total viral area under the curve (vAUC) for virologic shedding as measured by quantitative PCR (qPCR) for MVA-NP+M1 vs. Placebo groups.

Secondary endpoints include:

- Incidence in each group (MVA-NP+M1 and saline Placebo) of laboratory-confirmed ILI (qPCR or culture)
- Total AUC for total symptom score for MVA vs. Placebo
- Total days of fever for MVA-NP+M1 vs. Placebo
- Total mucus weight for MVA vs. Placebo
- Correlation of T cell responses (as defined by ELISpot assay) to the primary endpoint, symptom scores, and influenza incidence
- The attack rate, defined as percentage of inoculated participants with at least two positive swabs as determined by qPCR

Exploratory endpoints

- Time to start; time to peak and duration of qPCR and quantitative culture results
- Time to start, time to peak, and duration for total symptoms for MVA vs. Placebo
- Severity of individual symptoms for MVA-NP+M1 vs. Placebo

- Correlation of antigen specific T cell phenotypes to the primary endpoint, symptom scores, and influenza incidence
- Effect of vaccination on the antibody responses to influenza following the intranasal challenge
- Transcriptional response to vaccination and viral challenge assessed by deep sequencing of RNA
- Potential assessment of epigenetic responses of T-Cells during the study.

Safety

- Frequency and severity of participant-recorded local and systemic adverse events recorded for the 7 days following vaccination
- Frequency and severity of non-solicited adverse events captured throughout the study after vaccination
- Frequency and types of serious adverse events
- Severity of adverse events in each study group following intranasal challenge with H3N2

Statistical Methods:

Sample size: determined by the challenge cohort of N=134

Immune response:

Primary immune endpoint will be the T cell response measured by ELISpot and recorded as the mean spot forming units per million peripheral blood mononuclear cells (PBMCs) in the peptide-stimulated wells minus the mean dimethyl sulfoxide (DMSO) control wells for the given sample.

Efficacy:

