2. STUDY OBJECTIVES

2.1 PRIMARY OBJECTIVE

The primary objective of the study is to determine the efficacy of MVA-NP+M1 vaccine administered in a human influenza challenge model to reduce the degree of nasopharyngeal viral shedding (recorded as viral AUC as determined by qPCR).

Hypothesis: The primary hypothesis tested in this study is that the induction of influenza-specific CD4+ and CD8+ T cells by MVA-NP+M1 will result in a decrease of the viral replication and symptoms associated with influenza following challenge with an H3N2 influenza A virus in healthy volunteers.

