9. STATISTICAL METHODS

9.1 STATISTICAL ANALYSIS

No formal interim analyses are planned for this trial.

Statistical analyses will be performed by a qualified vendor under the supervision and responsibility of the Sponsor, using SAS® (SAS Institute Inc., Cary, NC, USA; version 9.2 or higher) and/or Phoenix™ WinNonlin® (Pharsight Corporation, Palo Alto, CA, USA; version 6.1 or higher). Unscheduled interim analyses may be performed at the request of the IDMC to monitor the safety of the investigative vaccine throughout the study (also Section 5.7). Details will be described in a separate IDMC charter.

The following populations will be considered for analysis:

- intent-to-treat (ITT) population, defined as all randomized participants who received the challenge inoculation, according to the assigned (randomized) treatment group

- per-protocol (PP) population, consisting of a subset of the ITT population without any major protocol deviations and including those participants who remain in the quarantine facility for the full extent of the challenge phase
- safety population, consisting of all participants vaccinated in the vaccine phase, according to the vaccination actually received
- challenge safety population, which includes all of those in the above defined ITT, according to the vaccination actually received.

Unless specified otherwise, the ITT population will be used for efficacy and immunogenicity analysis. The safety populations will be used for safety/tolerability analysis and analysis of demographics.

All statistical methods shall be detailed in a Statistical Analysis Plan (SAP) to be issued by SGS statistical team and finalized before database lock. The SAP will be approved by the Vaccitech Ltd statistical consultant.

The final efficacy analysis will be performed once all participants have completed 27 days from the time of inoculation (Day 28 post-challenge) or 6 months post-vaccination, whichever is last.

For continuous variables, descriptive statistics will include mean, standard deviation (SD), median, minimum, maximum, and range. For categorical variables, descriptive statistics will include frequencies and percentages.

9.1.1 *Baseline Characteristics*

For all participants who undergo vaccination, descriptive statistics will be provided per vaccination group for demographic (e.g. age, height, weight, BMI, race, sex) and other initial participant characteristics (physical examination, medical and surgical history, concomitant diseases).

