T cell responses (as defined by ELISpot assay) will be evaluated in relation to the primary endpoint, symptom scores and influenza incidence.

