1.1 STUDY OBJECTIVES

According to the protocol, the primary objective of this study is to determine the efficacy of MVA-NP+M1 vaccine administered in a human influenza challenge model to reduce the degree of nasopharyngeal viral shedding (recorded as viral area under the curve (AUC) as determined by quantitative polymerase chain reaction (qPCR)).

The primary hypothesis tested in this study is that the induction of influenza-specific CD4+ and CD8+ T cells by MVA-NP+M1 will result in a decrease of the viral replication and symptoms associated with influenza following challenge with an H3N2 influenza A virus in healthy volunteers.

According to the protocol, the secondary objectives of this study are to determine:

- The incidence in each group (MVA-NP+M1 and saline Placebo) of laboratory-confirmed influenza (qPCR or culture)
- The attack rate, defined as percentage of inoculated participants with at least two positive swabs as determined by qPCR
- Total AUC for total symptom score for MVA-NP+M1 vs. Placebo
- Total days of fever for MVA-NP+M1 vs. Placebo
- Total mucus weight for MVA-NP+M1 vs. Placebo
- Correlation of T cell responses (as defined by ELISpot assay) to the primary endpoint, symptom scores, and influenza incidence
- Safety of MVA-NP+M1 vaccination
- Safety of H3N2 challenge in the setting of MVA-NP+M1 vaccination

	Statistical Analysis Plan	
FLU010	Final analysis	Final 3.0 of 15JUN2020

According to the protocol, exploratory objectives are to determine:

- Time to start; time to peak and duration of qPCR and quantitative culture results
- Severity of individual symptoms for MVA-NP+M1 vs. Placebo
- Time to start, time to peak, and duration for total symptom score for MVA-NP+M1 vs. Placebo
- Correlation of antigen specific T cell phenotypes with illness outcomes
- Effect of vaccination on the antibody responses to influenza following the intranasal challenge
- Transcriptional response to vaccination and viral challenge assessed by deep sequencing of RNA
- To determine the epigenetic response of different cell subsets to influenza infection.

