2.2.4 Presentation of results

To assess the impact of missing DMSO replicates, all tables and figures on T-cell response will be prepared on two subsets of data (evaluated separately for NP and M1):

- Samples with at least 1 result
- Subset above, excluding samples with only 1 DMSO replicate result

Background subtracted and negative control T cell response results (IFN-gamma and granzyme B results; separately for NP, M1, NP+M1) will be summarised by means of descriptive statistics at each analysis visit. This will be done separately for the vaccination and challenge period. Actual values and changes from baseline will be tabulated separately.

T cell responder status will be presented in a frequency table at each analysis visit, separately for vaccination and challenge period.

Antibody response results will be summarised by means of descriptive statistics at each analysis visit. Actual values and changes from baseline will be tabulated separately. The ratio (MVA-NP+M1 / placebo) of the geometric means will also be shown with corresponding 95% CI.

Correlation of T cell responses, as assessed by the mean increase from baseline to post vaccination at day 8 and day 28 (for IFN-gamma and granzyme B results; separately for NP, M1, NP+M1), to the primary endpoint, symptom scores, and influenza incidence will be explored graphically, including Spearman correlation coefficients.

Graphs of the median actual values over time will be prepared for background subtracted and negative control IFN-gamma and granzyme B results (separately for NP, M1, NP+M1).

	Statistical Analysis Plan	
FLU010	Final analysis	Final 3.0 of 15JUN2020

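### SAP 2.2.1 drops the T-cell analyses if ELISpot results miss the final analysis, with no provision to run them later, although the protocol commits to them without condition

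*SAP*

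**What the plan says.** SAP 2.2.1 (immunogenicity, available data) describes the ELISpot assay and then states: "ELISpot assay results will possibly not be available for the final analysis". The next sentence gives the consequence: "In that case, analyses of the T cell response described below will not be done".

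SAP 1.1 nevertheless restates the protocol's secondary objective: "Correlation of T cell responses (as defined by ELISpot assay) to the primary endpoint, symptom scores, and influenza incidence". Protocol 2.2 lists the same objective, and the protocol synopsis lists it as a secondary endpoint. Protocol 9.1.2.2 turns it into an analysis commitment: "T cell responses (as defined by ELISpot assay) will be evaluated in relation to the primary endpoint, symptom scores and influenza incidence". No condition is attached in any of these places.

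Two further statements give ELISpot its weight. The synopsis, under statistical methods, says: "Primary immune endpoint will be the T cell response measured by ELISpot". The primary hypothesis in Protocol 2.1 is that "the induction of influenza-specific CD4+ and CD8+ T cells by MVA-NP+M1 will result in a decrease of the viral replication".

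On timing, Protocol 9.1 says: "The final efficacy analysis will be performed once all participants have completed 27 days from the time of inoculation", or have reached 6 months after vaccination, whichever comes last.

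**The concern.** The SAP foresees that the assay data may be missing at the final analysis and answers by omitting the analyses instead of postponing them. A secondary objective that the protocol states without condition thus becomes conditional in the SAP.

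What is at stake is how the trial can be read. The vaccine is meant to act through T cells. If vAUC shows no difference and no T-cell data are reported, a reader cannot tell a vaccine that failed to raise T cells from one that raised them without affecting shedding. If vAUC does differ, the proposed mechanism goes unexamined. The antibody assays (MNT and HI) do not answer either question.

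**Working it through.** No power or error-rate calculation applies. The check compares the passages, counts the affected displays and works out one time interval.

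**1. What the sentence removes.** The T-cell content after it consists of:
- SAP 2.2.2: background-subtracted responses, negative-control results and permutation-based responder status.
- SAP 2.2.3: the ANCOVA on T-cell response and the Fisher test on responder status.
- SAP 2.2.4: descriptive tables, responder frequencies, median plots and the analysis that serves the secondary objective, which begins "Correlation of T cell responses, as assessed by the mean increase from baseline to post vaccination at day 8 and day 28" and is explored graphically with Spearman coefficients.

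In SAP section 8 the displays that need ELISpot data are tables 14.2.4.1 to 14.2.4.3, figures 14.2.4.1 to 14.2.4.3 and listing 16.2.6.5: 3 + 3 + 1 = 7. Section 8 lists them without the condition. The antibody displays are not affected.

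**2. What the protocol requires.**
- Correlation of ELISpot with vAUC, symptoms and incidence: secondary objective (2.2), secondary endpoint (synopsis), unconditional analysis (9.1.2.2).
- ELISpot response itself: primary immune endpoint (synopsis). The between-group comparison stands under exploratory endpoints in 9.1.2.3, so only the correlation carries secondary status.

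**3. Whether late results would have to end the analysis.** Protocol 3.1 schedules blood for immunogenicity on Days 1, 8 and 28 after vaccination, on entry for challenge and on Day 28 after challenge. SAP 2.2.1 names the same five occasions for ELISpot, labelling the first one day 0. The last coincides with one arm of the final-analysis trigger, so no scheduled sample falls after it.

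The correlation in SAP 2.2.4 uses only the change from vaccination baseline to Days 8 and 28. With the windows in Protocol 7.1:
- latest Day 28 vaccination visit: 27 + 3 = 30 days after vaccination;
- earliest 6-month contact: 180 − 14 = 166 days after vaccination;
- margin: 166 − 30 = 136 days.

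Because the trigger takes the later of the two follow-up points, each participant's samples for the correlation are due at least 136 days before that participant's follow-up is complete. Protocol 7.1.6 says the assay is run on cryopreserved PBMCs, so a late result is not in itself a lost result.

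**4. Whether a fallback stands elsewhere.** SAP 1.5 (topline), 5.3.1 (missing values) and 6.1 to 6.3 (changes), and Protocol 7.1.6, 9.1 and 9.1.2, contain no deferred run, addendum, supplementary report or instruction to hold the analysis for the assay. Intracellular cytokine staining is optional in Protocol 7.1.6, and the SAP specifies no analysis of it that could stand in.

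**5. Whether the condition is defined.** It is not. No date and no proportion of samples says when results count as unavailable.

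**The case against.** The strongest reply is about scope. SAP section 1 limits the document to the final analysis, and the sentence speaks only of that analysis. A reader might infer that the SAP forbids T-cell analysis or abandons it for good. The text does not support this: it plans nothing later, but it prohibits nothing. Nor does Protocol 9.1 oblige the sponsor to analyse as soon as follow-up ends, since the trigger is an earliest point and not a deadline.

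The risk may also be small. SAP 2.0 rebuilt the per-pool derivation and the responder rule. SAP 3.0 added a second sample subset at the sponsor's request and a seed for the permutation code. These revisions suggest that the analyses were expected to run. That is inference, but reasonable. Both points stand; neither supplies the missing provision.

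Four further readings are tempting and should not be drawn:
- *That a later run would be a post-hoc choice made with the efficacy result in hand.* Topline vAUC is unblinded at group level before database lock (SAP 1.5), and no T-cell display is flagged for topline. But the derivations, tests and seeded code are already fixed in a dated SAP, so running them unchanged selects nothing.
- *That the loss can be sized as power for a correlation.* The SAP specifies no correlation test, significance level or target coefficient, so a power figure would describe an analysis that is not planned.
- *That only laboratory turnaround could be outstanding.* The SAP gives no reason for unavailability. Limited cell yield (Protocol 7.1.6) and missing DMSO replicates (SAP 2.2.4) are both foreseen, and deferral cures neither.
- *That the not-applicable entry in SAP 6.1 is an error.* A disclosed contingency that has not occurred is not yet a change to the planned analysis.

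**Conclusion.** The point holds as a conflict between an SAP rule and an unconditional protocol commitment. If the rule is applied, all seven ELISpot displays are dropped from the final analysis, one secondary objective goes unanswered, the primary immune endpoint is unreported, and a null vAUC result becomes hard to interpret. The primary Mann-Whitney comparison of vAUC and the symptom, antibody and safety analyses do not depend on ELISpot and are untouched.

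The conclusion rests on two assumptions: that the rule would be followed as written, and that unavailability would at least sometimes mean lateness and not unusable samples. The documents do not say how likely either is. This is a cheap improvement to the plan, not a threat to the main result.

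**What to change.** Replace the cancelling sentence in SAP 2.2.1 with:

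*If ELISpot results are not available at database lock, the T-cell analyses in sections 2.2.2 to 2.2.4 will be run unchanged and reported as a pre-specified addendum when the assay data are transferred.*

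This also ties the condition to a defined point, database lock. If the analyses are in the end omitted, declare that in SAP section 6 as a departure from the protocol. No new blinding rule is needed, because Protocol 3.2 already has the immunology laboratories receive blinded samples and report in a blinded fashion.

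The cost is one SAP sentence and, if the data are late, an addendum to the clinical study report.

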  set permresults;  
  if 0 lt perm_p lt 0.05 then RESPSTAT = 1;  
  else if perm_p ge 0.05 then RESPSTAT = 0;  
run;
```

	Statistical Analysis Plan											
	FLU010											Final 3.0 of 15JUN2020

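### As coded, the T-cell responder rule can never call an M1 responder when only one DMSO well is available, and with full duplicates it misses most strong responses confined to one M1 pool

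*SAP*

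**What the plan says.** SAP 2.2.1 sets out the assay: "three stimulation antigens will be assessed: NP (4 pools), M1 (2 pools) and a negative control (DMSO"). On replication it states that "the number of spot-forming colonies (SFC) per well (i.e. 200,000 cells) will be reported for two replicate wells".

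SAP 2.2.2 compares each pool's wells "against the negative control replicate wells using a two-sample t-test". Within each antigen, "the observed SFCs/well will be permuted across all the peptide pool and negative control wells 100,000 times", and the lowest p-value of each permutation is kept for the adjustment. The decision rule, applied separately to NP and M1, is: "If a permutation-adjusted p-value of any of the pools within the antigen is less than 0.05, then the subject will be considered a responder". The section adds that significance needs enough permuted outcomes, but it sets no minimum and no consequence.

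The code in SAP 9.1 runs an upper-tailed permutation in PROC MULTTEST. It scores 1 only when the adjusted p is above 0 and below 0.05, and otherwise "else if perm_p ge 0.05 then RESPSTAT = 0".

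SAP 6.3 records that version 3.0 dropped the need for at least two replicates when deriving responder status. SAP 2.2.4 instead presents every T-cell table on two data subsets: samples with at least one result, and "Subset above, excluding samples with only 1 DMSO replicate result".

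**The concern.** A permutation p-value cannot fall below a floor set by the number of distinct ways of relabelling the wells. With five or six wells that floor is close to or above 0.05, so a sample can be labelled a non-responder because of plate layout and not because the response is weak.

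Responder rate is the SAP's only pre-specified yes/no summary of T-cell response, for a vaccine whose primary hypothesis is T-cell induction (SAP 1.1). If M1 status depends partly on well loss and on noise among low wells, Table 14.2.4.3 understates how many participants responded, and the Fisher test (SAP 2.2.3) loses power. Because version 3.0 dropped the replicate requirement, the comparison of the two subsets, which is meant to show the effect of missing DMSO wells, adds only forced zeros for M1 responder status.

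**Working it through.** The documents give no sensitivity or minimum p for this rule, so there is no stated figure to reproduce.

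**Inputs**
- Two M1 pools and four NP pools, two wells each (SAP 2.2.1).
- Two DMSO wells in a complete sample. This is inferred: SAP 2.2.4 treats one DMSO replicate as the incomplete case.
- Upper-tailed test, responder if any pool's adjusted p is below 0.05 (SAP 2.2.2 and 9.1).
- Assumed: ties counted, the usual permutation convention, and variance pooled over all groups as the behaviour of the coded procedure.
- Assumed: Poisson counts at the means shown. The documents give no SFC levels.

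**Number of arrangements** = N! / (product of group sizes!)
- M1, one DMSO well: 5!/(1!2!2!) = 30
- M1, two DMSO wells: 6!/(2!2!2!) = 90
- NP, two DMSO wells: 10!/(2!)^5 = 113,400

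**Floor for M1.** Swapping the two pool labels leaves the minimum p unchanged, so arrangements come in pairs.
- One DMSO well: 2/30 = 0.067, above 0.05.
- Two DMSO wells: 2/90 = 0.022.

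More random draws cannot lower these values. Enumerating all 30 arrangements for simulated one-DMSO samples, including both pools at 100 SFC/well, gave 0% responders in every scenario.

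**One M1 pool strong, the other at background, two DMSO wells.** The two high wells stay together in a pool in 2 × 4!/(2!2!) = 12 of the 90 arrangements. The adjusted p therefore lies between 2/90 and 12/90 and moves in steps of 2/90: 0.022, 0.044, 0.067 and so on. Only the first two steps are below 0.05. The step reached depends on how the four low wells happen to split, and ties among low counts push p up.

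Example: DMSO 0, 0; pool 1 100, 100; pool 2 0, 0. All 12 arrangements tie, so p = 12/90 = 0.133. The response is 5 × 100 = 500 SFC per million, and it is scored as a non-response.

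**Simulated M1 detection, two DMSO wells, full enumeration**

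| DMSO background | Pool A | Pool B | Called responder |
|---|---|---|---|
| 0.5 | 0.5 | 50 or 100 | about 12–13% |
| 2 | 2 | 50 or 100 | about 27% |
| 2 | 5 | 100 | about 75% |
| 2 | 10 | 100 | about 98% |
| 2 | 20 or 50 | 100 | 100% |
| 2 | 100 | 100 | about 61–62% |

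Across repeated runs with background 0.5–2, the one-pool case gave 12–29% and two equally strong pools about 61–65%. Wider assumptions (background up to 5, 5% overdispersion, two-sample instead of pooled variance) gave 16–31% for the one-pool case.

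**NP, one strong pool, two DMSO wells.** The high wells stay together in 4 × 8!/(2!)^4 = 10,080 arrangements, so p can reach 10,080/113,400 = 0.089. Simulated detection was 43–59%, about half.

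**The case against.** **The rule does work in many samples.** A reader might infer that it cannot work with duplicate wells at all. The figures above do not support that: with two DMSO wells the M1 floor is 0.022, and detection reaches 98–100% once the second pool is raised to a clearly different level. The low figure needs the other pool at background. This stands, and it limits the point.

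**The DMSO count is inferred.** Protocol 7.1.6 leaves the plate layout to the laboratory manual. With more DMSO wells a one-pool M1 response is found more often: roughly 44–47% with three wells, 61% with four and 100% with six. This stands as a condition on the 90-arrangement result. It does not rescue samples left with one DMSO well.

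**The text differs from the code.** SAP 2.2.2 counts permuted values strictly below the observed one. Read literally, p = 0 becomes possible and 35–54% of strong one-pool M1 responses would be called with one DMSO well. False positives with no response would then be about 12–14%, against about 8–9% with two DMSO wells. The code leaves p = 0 unscored, so as programmed there is still no M1 responder. The result therefore holds for the code with ties counted, and the conflict is a further reason to amend.

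**Single-DMSO samples are partly handled.** The second subset drops them. That is true, but the first subset still reports them as non-responders and not as undetermined.

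**The T-cell evidence as a whole is not compromised.** A reader might infer that a misclassified variable reaches the mechanistic analyses. It does not: the ANCOVA in SAP 2.2.3 and the correlations in SAP 2.2.4 use continuous counts. SAP 2.2.1 also allows that the T-cell analyses may not be done at all in the final analysis.

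**Conclusion.** The concern holds for M1 responder status as coded, in two parts.

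1. With one DMSO well, a responder call is impossible (minimum p 0.067) and the sample is recorded as a non-responder. This rests only on the layout and on counting ties.
2. With two DMSO wells, a strong response in one M1 pool with the other at background is called only about 12–29% of the time, whatever its size. This also rests on the inferred two DMSO wells and on the assumed Poisson backgrounds of 0.5–2 SFC/well.

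NP has ample arrangements but still misses about half of one-pool responses.

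The effect is confined to Table 14.2.4.3 and its Fisher test. How far the reported rates would move cannot be stated, because the documents do not say how many samples have one DMSO well or how often a response sits in a single pool. The documents do not support the broader conclusions that the rule fails on all duplicate data or that the trial's T-cell findings or primary result are at risk.

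**What to change.** 1. In SAP 2.2.2 and the code, set responder status to missing, not 0, wherever the smallest attainable adjusted p is 0.05 or more. For M1 this covers samples with one DMSO well. Report the number of undetermined samples by arm and visit.
2. Reconcile the strict inequality in the SAP 2.2.2 text with the code, which requires an adjusted p above 0, and state how ties are counted. State the number of DMSO wells in a complete sample.
3. Before responder results are seen by arm, replace the rule or add a sensitivity analysis suited to duplicates. One option is a one-sided exact conditional comparison of total pool spots with total DMSO spots, with the number of wells as exposure and Holm adjustment within antigen. Combine it with a minimum background-subtracted difference in SFC per million, set from Day 1 samples. A difference is preferable to a fold-change because it remains defined when DMSO is zero.

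The first item is about one line of code; the rest is SAP wording and a short program on existing data. The downside is that the exact count test ignores extra well-to-well variation, which the minimum difference is meant to offset.
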